4 STUDY DESIGN

This clinical study is a phase 4, single-site, open-label PK and pharmacodynamic (PD) study of IV artesunate in up to 100 Ugandan children 6 months-14 years of age who are diagnosed with severe malaria according to standardized WHO criteria (any *P. falciparum* parasitemia and the presence of danger signs).

Treatment

Participants will receive the standard of care with IV artesunate (Guilin Pharmaceutical Factory, Guangxi, People's Republic of China), for treatment of severe malaria per WHO guidelines. Artesunate will be reconstituted as follows:

- 30 mg vial of artesunate powder will be dissolved in 0.5 mL sodium bicarbonate and provided in the pack to form sodium artesunate and then mixed with 2.5 mL of sodium chloride (9mg/ml for injection).
- 60 mg vial of artesunate powder will be dissolved in 1 mL sodium bicarbonate and provided in the pack to form sodium artesunate and then mixed with 5 mL of sodium chloride (9mg/ml for injection).
- 120 mg vial of artesunate powder will be dissolved in 2 mL sodium bicarbonate and provided in the pack to form sodium artesunate and then mixed with 10 mL of sodium chloride (9mg/ml for injection).

This will be injected as a bolus into an indwelling IV cannula.

Dosage of Artesunate

Children weighing <20 kg will receive IV artesunate at a dose of 3.0 mg/kg/dose compared to older children weighing $\geq 20\text{kg}$, who will receive 2.4 mg/kg/dose, at times 0, 12, 24, After the initial 24 hours of IV artesunate, children will be assessed clinically and for ability to take oral medications. If unable to take oral medication, IV artesunate will continue at 48 and 72 hours (WHO 2015). Children who recover and are able to transition to oral antimalarial therapy after a minimum of 24 hours or later, will initiate a 3-day course of oral artemisinin-combination therapy per national guidelines. Participants will be given standardized instructions by a nurse on how to take the artemether-lumefantrine regimen according to standard practice and told that all doses should be taken 30 minutes to 1 hour after food, preferably containing fat or oil.

Variables

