3.3. Study Definitions and Derived Variables

Severe Malaria

Severe malaria is defined as presence or history of fever plus a positive blood film for *P. falciparum* malaria with at least one of the following symptoms and signs:

- Repeated convulsions: More than two episodes within 24 h
- Impaired consciousness: A Blantyre coma score < 3 in children
- Coma
- Hyperpyrexia: Axillary temperature $\geq 40^{\circ}\text{C}$
- Respiratory distress: Acidotic breathing
- Inability to tolerate oral therapy and vomiting all oral intake
- Circulatory collapse or shock: Systolic blood pressure < 50 mmHg in children
- Spontaneous bleeding
- Hemoglobinuria: Hemoglobinuria presents as tea colored urine
- Jaundice
- Prostration: Extreme weakness so that the person is unable to sit, stand or walk without assistance
- Severe normocytic anaemia: Hemoglobin concentration < 5 g/dL
- Hypoglycemia: Blood or plasma glucose < 2.2 mmol/L (< 40 mg/dL)
- Renal impairment: Plasma or serum creatinine > 265 $\mu\text{mol/L}$
- Hyperparasitemia: *P. falciparum* parasitemia > 10%

Whether participants meet this definition of severe malaria will be evaluated in the process of determining enrollment eligibility. Participant history of fever, indication of positive blood film for *P. falciparum* malaria, and the presence of additional assessed symptoms and signs of severe malaria will be documented in the appropriate electronic case report form (eCRF). Only one additional sign or symptom of severe malaria must be present along with history of fever and positive blood film for *P. falciparum* malaria for a participant to meet the definition of severe malaria. Once a participant meets the definition of severe malaria, investigators may opt not to assess the participant for additional signs and symptoms. Reported symptoms and signs of severe malaria at enrollment will be summarized in [Table 6](#).

Baseline

Baseline values of primary outcome measures of physiological dysfunction, laboratory parameters, and vital signs will be defined as the most recent measurement before first dose of IV artesunate. If these measurements are not collected before first dose, such as for participants who received IV artesunate before enrollment, baseline values will be defined as either the screening measurement or the earliest measurement after first dose of IV artesunate, whichever is closest to time of first dose of IV artesunate.

Weight-for-Age and Height-for-Age Z-Scores

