6.4. Covariates and Subgroups

Sensitivity analyses for the primary and both secondary analysis outcome measures will be conducted to assess the effect of receipt of IV artesunate or other artemisinin-based therapies before enrollment on results of the primary and secondary analyses. This sensitivity analysis will be conducted on the subset of the PD Analysis Population who did not receive any IV artesunate or other artemisinin-based therapy before enrollment.

Otherwise, the protocol does not define any formal subgroup analyses, and the study is not adequately powered to perform subgroup analyses. However, primary and secondary analyses will be adjusted for

possible confounding factors. The following baseline covariates will be considered for inclusion in all primary and secondary analyses:

- Sex (male or female),
- Weight group (<20 kg or \geq 20 kg),
- Receipt of IV artesunate or artemisinin-based therapy before study enrollment (received no IV artesunate or artemisinin-based therapy before study enrollment or received any IV artesunate or artemisinin-based therapy before study enrollment), and
- Receipt of antimalarial concomitant medications or other concomitant medications with antimalarial properties (received no such concomitant medications or received any such concomitant medications).

Receipt of oral ACT post-enrollment (received no oral ACT or received any oral ACT) will also be considered for inclusion as a covariate in primary analyses at timepoints at which there are participants receiving oral ACT and in secondary analyses. The number of doses of oral ACT received may also be considered for inclusion in these analyses.

Inclusion of covariates in each primary and secondary analysis will be informed by exploratory boxplots and stacked bar graphs of response variables by covariate values, and by timepoint when appropriate (see Section 8 for further details).

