6.5. Missing Data

Every effort will be made to minimize missing data and collect all outcome measures specified in this protocol. Participants who discontinue treatment will be followed after treatment discontinuation for collection of all scheduled follow-up data with their consent.

Missing dose data (dosing time, or dosing date) will be imputed to maximize the inclusion of observations subsequent to doses with missing information. Missing dosing time will be imputed if the dose date and amount are available:

- If dosing times are missing, the pre-dose sample time combined with the dose number and dosing timeline will be used to determine the pre-study and on-study dosing times.
- Dosing time will be imputed as the mean of the time from pre-dose draw to dosing for those not missing the given sampling window.

Missing covariate data for analyses that incorporate confounding covariate variables will be handled in the following manner. The covariate will be excluded from the analysis if more than 20% of the covariate values are missing. Baseline individual covariates, including sex and weight group, will be determined from the Day 1 visit. If an individual's baseline covariate is missing at the Day 1 visit, the baseline covariate value will be taken from either the pre-study (screening) visit or from the earliest post-dose visit, whichever is closest to the baseline visit. Receipt of IV artesunate or artemisinin-based therapy before enrollment will be determined from treatment administration records with dates and times before the first on-study dose and/or concomitant medication records with dates up to the Day 1 visit. Receipt of oral ACT, which has planned collection occurring after baseline, will be determined from all visits up to and including the visit at which the analysis timepoint occurs.

No imputation will be performed for missing primary or secondary PD outcome response variables. Rather, only participants in the PD Analysis Population with the PD outcome response variable measured at the timepoint of interest will be included in PD analyses of that PD outcome response variable measured at the timepoint of interest.

Please refer to the Pharmacometrics Analysis Plan for details pertaining to methods for missing concentration data and other missing data that would affect the PK analysis.

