## Mean and Standard Deviation of EC50, for example ##
mean(fit_param$ec50)
sd(fit_param$ec50)
```

Exploratory scatterplots for the response outcome measure at each timepoint given the exposure measure will be utilized to assess whether a log-transformation of the response variable may be necessary. These exploratory scatterplots as well as goodness of fit diagnostic plots will be used to assess reasonableness of model assumptions. If Emax model assumptions seem unlikely to hold, linear or polynomial models will be considered as informed by the exploratory scatterplots.

A linear model for primary outcome effect, E_i , is defined as follows:

$$E_i = E_{0,i} + \beta P_i + \eta^T X_i + e_i,$$

where E_i represents the given response outcome measure for the i th participant at the given timepoint, $E_{0,i}$ is the baseline response outcome measure for participant i , P_i is the exposure parameter value for participant i , X_i are the values of the additional covariates included in the model, and e_i are the measurement errors for participant i . These measurement errors are assumed to be independent and normally distributed with mean zero and nonzero variance. In addition to the covariates listed in Section 6.4, actual time of response measurement post-first dose will also be considered for inclusion in the model.

If linear models are fit for a primary outcome effect, the following pseudocode will be used for model fitting and to extract p-values for the exposure model parameter.

```
/* Linear model fit and output p-values */
proc glm data=dataset(where=(population=p and response=r));
*catvar = any categorical covariates included in the model;
*refvalues = the value(s) to be used as the reference level for categorical
covariate(s);
class catvar(ref=refvalues);
*baseresp = response at baseline;
*othercovars = any other covariates (including those specified in the class statement)
included in the model;
model resp = baseresp exposure othercovars / noint ss3;
by timepoint;
ods output ModelAnova=tests3;
run;
data tests3; set tests3(where=(source='EXPOSURE')) ;
rename ProbF=pval;
run;
```

A polynomial model for primary outcome effect, E_i , is defined as follows:

$$E_i = E_{0,i} + \sum_{j=1}^a \beta_j P_i^j + \eta^T X_i + e_i,$$

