**Step 5: END**

6. End.

PCT_{50} and PCT_{90} for each participant will then be estimated using the formulas described previously in this section. Individual estimates of K and t_{lag} will be presented in [Listing 15](#). The following pseudocode will be used to fit cubic normal and tobit regression models and to calculate model-predicted values for each participant's log-parasite density data.

```

/* Cubic Regression with Predicted Values by Participant ID */
data clearance; set clearance;
time2=time**2; time3=time**3;
log_density=log(density);
run;
proc reg data=clearance;
model log_density=time time2 time3 / p;
  
```

```

by partid;
ods output OutputStatistics=predicted;
run;

/* Cubic Tobit Regression with Predicted Values by Participant ID */
data clearance; set clearance;
time2=time**2; time3=time**3;
log_density=log(density);
/*replace parasite density values = the lower limit for the variable with.*/
if density=LOD then lower=.;
else lower=log_density;
run;
proc lifereg data=clearance outest=OUTEST(keep=partid _scale_);
  model (lower, log_density) = time time2 time3 / d=normal;
  by partid;
  /*output mean of uncensored variable*/
  output out=OUT xbeta=Xbeta;
run;
data predict; merge out outest; by partid;
  lambda = pdf('NORMAL',Xbeta/_scale_);
  / cdf('NORMAL',Xbeta/_scale_);
  /*calculate mean of censored variable*/
  predict = cdf('NORMAL', Xbeta/_scale_)
    * (Xbeta + _scale_*lambda);
run;

```

Total parasite clearance by Day 2 will be a binary variable indicating whether total parasite clearance has occurred within the first 50 hours post-first dose of IV artesunate. Total parasite clearance will be determined using all thick blood smears collected within the 50 hours from the first dose of IV artesunate. Total parasite clearance by Day 2 will be determined for participants in the PD Analysis Population with any results of thick blood smears available within 50 hours after the first dose of IV artesunate.

The relationship between AUC_{0-12} , C_{max} , $t_{1/2}$ and T_{max} , and the time-to-event response variables of PCT_{50} and PCT_{90} will be analyzed using Cox proportional hazards regression. One Cox proportional hazards regression model will be fit for each response variable and DHA exposure parameter. Covariates in these models will include the appropriate exposure parameter as well as a subset of the covariates given in Section 6.4.

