Table 22: Model Specifications for Assessments of Relationships between Time to Hospital Discharge and Exposure Parameters by Exposure Parameter and Analysis Population

[Implementation Note: Model Type will Cox Proportional Hazard. Covariates Included in the Model will at minimum include Exposure Parameter and Actual Time of Collection, but may also include Sex, Weight Group, Receipt of IV Artesunate or Other Artemisinin-Based Therapy Before Enrollment, Receipt of Concomitant Medications, and Receipt of Oral ACT.]

Analysis Population	PK Exposure Parameter	Model Type	Covariates Included in the Model
PD Analysis Population (N=X)	AUC ₀₋₁₂ (N*=X)		
	C _{max} (N*=X)		
	T _{max} (N*=X)		
	t _{1/2} (N*=X)		
PD Analysis Population, No Prior IV Artesunate or Other Artemisinin-Based Therapy Subset (N=X)	AUC ₀₋₁₂ (N*=X)		
	C _{max} (N*=X)		
	T _{max} (N*=X)		
	t _{1/2} (N*=X)		

Notes: N = Number of participants in each analysis population or subset for which time to first hospital discharge can be calculated. N* = Number of participants in each analysis population or subset with estimable PK exposure parameter and for which time to first hospital discharge can be calculated.

Time of hospital discharge is calculated as the time in days from time of initial participant admission to the time of first discharge.

Table 23: Parasite Density Summary Statistics by Timepoint and Analysis Population

Analysis Population	Planned Timepoint ^a	N	Parasite Density (# Parasites per 200 WBC)			
			Mean	SD	Median	Min, Max
PD Analysis Population	0 (0-2) h	x	xx.xx	xx.xx	xx.xx	xx.x, xx.x
	6 (4-8) h	x	xx.xx	xx.xx	xx.xx	xx.x, xx.x
	12 (10-14) h	x	xx.xx	xx.xx	xx.xx	xx.x, xx.x
	24 (22-26) h	x	xx.xx	xx.xx	xx.xx	xx.x, xx.x
	36 (34-38) h	x	xx.xx	xx.xx	xx.xx	xx.x, xx.x
	48 (46-50) h	x	xx.xx	xx.xx	xx.xx	xx.x, xx.x
	Day 3	x	xx.xx	xx.xx	xx.xx	xx.x, xx.x
	Day 4	x	xx.xx	xx.xx	xx.xx	xx.x, xx.x
	Day 5	x	xx.xx	xx.xx	xx.xx	xx.x, xx.x
PD Analysis Population, No Prior IV Artesunate or Other Artemisinin-Based Therapy Subset	0 (0-2) h	x	xx.xx	xx.xx	xx.xx	xx.x, xx.x
	...					

Notes: N = Number of participants in the analysis population or subset with parasite density results available at the respective timepoint.

^a Timepoints are given post-first on-study dose of IV artesunate.

Table 24: Proportions of Total Parasite Clearance by Timepoint and Analysis Population

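### Secondary models may adjust for post-enrollment oral ACT, omit baseline parasite density for Day 2 clearance, and are told to include a collection time the outcomes do not have

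*SAP*

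**What the plan says.** **Oral ACT.** SAP 6.4 lists four baseline covariates for all primary and secondary analyses: sex, weight group, prior artemisinin, and concomitant medication with antimalarial effect. For the secondary analyses it then adds: "Receipt of oral ACT post-enrollment (received no oral ACT or received any oral ACT) will also be considered for inclusion as a covariate". It continues: "The number of doses of oral ACT received may also be considered for inclusion in these analyses". Section 8 repeats this as an option. Section 6.5 fixes the timing, with the last visit counted being that of the analysis timepoint: "Receipt of oral ACT, which has planned collection occurring after baseline, will be determined from all visits up to and including the visit". Protocol Section 4 says who gets oral ACT: "Children who recover and are able to transition to oral antimalarial therapy after a minimum of 24 hours or later". The Cox code in SAP 8.2.1 enters all covariates as fixed terms.

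**Day 2 clearance.** SAP 8.2.2 states: "Total parasite clearance by Day 2 will be a binary variable indicating whether total parasite clearance has occurred within the first 50 hours" after the first dose. Baseline parasite density is not named in 6.4, in 8, in 8.2.2 or in the table notes. The primary models do carry a baseline value; the linear-model code in 8.1 defines "baseresp = response at baseline". The baseline rule in SAP 3.3 covers physiological markers, laboratory parameters and vital signs. When no pre-dose value exists it falls back on the screening or earliest post-dose value, "whichever is closest to time of first dose of IV artesunate". Parasite density is not mentioned there.

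**Collection time.** The note to Table 22 says "Covariates Included in the Model will at minimum include Exposure Parameter and Actual Time of Collection". The notes to Tables 26 and 28 say the same. The text and equations in 8.2.1 and 8.2.2 contain no such term.

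**The concern.** The secondary objective is the relationship between DHA exposure and discharge, with no restriction to children at the same stage of recovery. Exposure is defined from the first on-study dose. Post-enrollment ACT comes later, so it cannot be a cause of exposure, but it can be a consequence of it through recovery. Adjusting for it may remove part of the effect being estimated. Covariates are chosen from plots of outcome by covariate, so ACT would look most attractive exactly when it tracks recovery.

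For Day 2 clearance, two children with the same clearance rate can have opposite outcomes because they started at different densities. Leaving density out costs power. It also confounds the odds ratio if density is correlated with exposure, which is observational here. Secondary tests have no multiplicity control.

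A programmer who follows the table notes literally would fit models that the SAP text does not define.

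**Working it through.** The documents give no power or effect size for the secondary models. The only stated power is for the primary tests (SAP Table 3); recomputing 24 tests at N=70 gives 0.802 against the stated 0.80. That figure does not bear on this point.

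**1. ACT in the discharge model.** The analysis timepoint in this model is discharge itself, so ACT status is read over the same follow-up that produces the outcome and is then entered as if known at the start. Dose count by discharge also partly measures length of stay.

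Illustration with assumed inputs: N=75, Cox with Breslow ties, 500 replicates per cell, median recovery 36 h, ACT at the next daily assessment from 24 h, lognormal stay after transition with median 30 h. Setting 1: 20% faster recovery per SD of exposure. Setting 2: 15% faster recovery plus 8% shorter stay after transition. Hazard ratios are per SD:

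| Setting | No ACT term | ACT term, 5% non-receipt | 10% | 20% |
|---|---|---|---|---|
| 1, slowest children get none | 1.31-1.33 (power 0.59-0.66) | 1.25 (0.41) | 1.21 (0.34) | 1.15 (0.23) |
| 2, slowest children get none | 1.35-1.38 | 1.32 | 1.30 | 1.27 |
| Non-receipt unrelated to recovery | 1.30-1.34 | no change | no change | no change |

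In the worst cell, ln 1.15 = 0.140 against ln 1.32 = 0.278, so the log hazard ratio is about halved. If every child gets ACT, the any/none term is constant. With dose count and every child on ACT, the hazard ratio goes from 1.32 to 1.46-1.47 in Setting 1 and stays at 1.34 in Setting 2.

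A second, separately built simulation (N=80, 150 replicates per setting, 63-81% receiving ACT) moved the log hazard ratio 5-21% toward the null in five of six settings, for example 1.44 to 1.34. The sixth gave no usable adjusted estimate.

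**2. Density and Day 2 clearance: arithmetic.** Inputs are the 40/µL detection limit and PCT50 = ln 2/K (SAP 8.2.2), with log-linear decline and no lag assumed. Clearance time is ln(P0/40)/K, and the highest density that clears by 50 h is 40·exp(50K).

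- K=0.15/h: threshold 40·exp(7.5) ≈ 72,300/µL. From 10,000/µL: ln(250)/0.15 = 36.8 h, cleared. From 200,000/µL: ln(5000)/0.15 = 56.8 h, not cleared.
- K=0.2/h: threshold 40·exp(10) ≈ 881,000/µL, so density matters less.

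PCT50 and PCT90 are functions of K alone, so this point does not extend to them.

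**3. Density and Day 2 clearance: simulation.** Assumed: N=75, 1500 replicates per cell, median P0 30,000/µL, SD of ln P0 1.2-2.0, median K 0.12-0.21/h with CV 30%, and an exposure effect of 12% on K per SD (0 for type I error).

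- Power rises by 1-18 points with log density (for example 0.53 to 0.62 when 64% clear), least when about 90% clear. The standard error of the log odds ratio also rises (0.272 to 0.329), so the gain is in power, not precision.
- With no true effect, unadjusted type I error at exposure-density correlation 0, 0.1, 0.2 and 0.3 is 4-5%, 5-8%, 7-17% and 12-32%. Adjusted, it is 3-6%.
- With 20-40% of children pre-treated and the first smear 0-24 h after first dose, density plus the prior-artemisinin indicator raises power from 0.52-0.53 to 0.58-0.60. At correlation 0.2-0.3 it holds type I error at 4-6%, against 10-24% unadjusted.
- ACT by 50 h barely moves the Day 2 result: log odds ratio 0.54 to 0.52, power 0.53 to 0.48.

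The second simulation (N=80, about 65% clearing) agrees: at correlation ±0.3, 13-27% false positives without density and 3-5% with it. A further run gave power 0.47 to 0.60, and type I error 22% against 5.5% at correlation 0.3 and 4% against 3% at 0.

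**4. Collection time.** Discharge is an interval from admission (SAP 4.5.1). PCT50 and PCT90 come from a fitted slope over several smears. Day 2 clearance pools all smears within 50 h; a clearance time exists only for children who clear, so using it would condition on the outcome. For discharge, any such time would be close to the outcome itself. In the primary models, where a measurement time does exist, the note to Table 19 makes it optional.

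**The case against.** ACT adjustment is optional, and Tables 22, 26 and 28 would disclose it. Nearly every child may receive ACT, which would make the any/none term almost constant. Part of the timing is administrative, through the 24 h minimum. Harm under any/none coding needs non-receipt concentrated in slow recoverers, and the documents give neither its rate nor its pattern. The direction is also unstable, since dose count pushes the hazard ratio away from 1. All of this limits the size and stands. It does not supply a reason to adjust for a post-exposure variable, and an answer that changes direction with the coding is itself a reason for leaving it out.

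On density, the confounding figures rest on an assumed correlation; at zero there is no type I error problem, only lost power. The arithmetic also assumes no lag and detection at exactly 50 h. Smears are timed from the first on-study dose, while the 50 h clock runs from the first dose. With a last smear at 48 h the threshold at K=0.15/h is 40·exp(7.2) ≈ 53,600/µL rather than 72,300. That moves the number but not the dependence on density; the power gain also appeared with a 48 h smear. If 90% of 75 children clear, only 7 or 8 do not, and the model becomes sparse. That caution stands.

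The collection-time point is editorial: it sits in notes to table shells. It is still a mandatory instruction that contradicts the text.

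SAP 8.1 also allows ACT in the primary models at first discharge. The calculations here do not cover those models, but the authors should settle the two uses consistently.

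**Conclusion.** The concern holds on all three parts, at the level of a change that should be made. The collection-time contradiction follows from the text alone. That baseline density helps decide Day 2 clearance follows from the SAP's own detection limit and 50 h cutoff; the power gain of 1-18 points and the type I error of 12-32% at correlation 0.3 rest on assumed densities, clearance rates and correlation. The ACT point rests on the order of events and on who receives ACT. Its size, from no change to roughly halving the log hazard ratio for discharge, depends on an unknown pattern of non-receipt and on simulations with assumed inputs. The case against ACT rests mainly on discharge, because its effect on Day 2 clearance is small. Confidence is medium.

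**What to change.** - **SAP 6.4, 6.5 and 8:** remove receipt and dose count of oral ACT from the main secondary models. If ACT is of interest, examine it as a time-varying covariate in a sensitivity analysis labelled as conditioning on a post-exposure variable.
- **SAP 8.2.2:** prespecify log baseline parasite density in the Day 2 clearance logistic model only. Extend the Section 3.3 baseline rule to density: the last smear before the first artesunate dose, otherwise the smear closest to it. Keep the prior-artemisinin covariate, and use the planned analysis without pre-treated children to check those whose first smear followed treatment.
- **Notes to Tables 22, 26 and 28:** delete Actual Time of Collection.

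The cost is SAP wording; no new data are needed. The Day 2 model spends one degree of freedom, which matters more if few children fail to clear. The adjusted odds ratio is conditional on density and will differ from the unadjusted one even without confounding. In pre-treated children, baseline density is partly affected by drug already given.
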